Document: \\IEEDC-NAS01A\Biosdata\Path\IVACFLU-S\IYA06804\Biostatistics \Documentation\SAP\IVACFLU-S-0203\_Mock\_Listings\_V1.0  
Author: [name]  
Version Number:  
Version Date:

1.0  
[11AUG2017]

Template No: CS\_TP\_BS016 Revision 4  
Effective Date: 01Apr2016

Reference: CS\_WI\_BS005

Copyright © 2009, 2010, 2012, 2016 Quintiles Transnational Corp. All rights reserved.  
The contents of this document are confidential and proprietary to Quintiles Transnational Corp. Unauthorized use, disclosure or reproduction is strictly prohibited.

TABLE AND LISTING MOCK SHELL

Listing 16.2.8.2  
Physical Examination - Vital Signs  
Full Analysis Population

Treatment	Subject ID/ Site ID/Age Group	Visit	Assessment Date	Vital Signs	Result	PE Finding/ Specify (e-CRF)	Grading Scale [a]
Vaccine	xxxxx/ xxxx/ xxxx	Screening	DDMMYYYY	Body Temperature (°C)	Xxx*	Normal	
Vaccine	xxxxx/ xxxx/ xxxx	xxxxx	DDMMYYYY	Systolic Blood Pressure (mmHg)	Xxx	Abnormal-NCS	
Vaccine	xxxxx/ xxxx/ xxxx	xxxxx	DDMMYYYY	Systolic Blood Pressure (mmHg)	Xxx	Abnormal-CS	3
Vaccine	xxxxx/ xxxx/ xxxx	xxxxx	DDMMYYYY	Pulse Rate (beats/min)	Xxx	Abnormal-CS/ xxxxxxxx	

CS: Clinically Significant; e-CRF: Electronic Case Report Form; PE: Physical Examination; NCS: Not Clinically Significant;  
[a]: Applicable only for Abnormal-Clinically significant PE findings.  
\*denotes the baseline result.

Programming Note: Sort by Treatment, Subject ID and Visit.

Document: \\IEEDC-NAS01A\Biosdata\Path\IVACFLU-S\IYA06804\Biostatistics \Documentation\SAP\IVACFLU-S-0203\_Mock\_Listings\_V1.0  
Author: [name]  
Version Number: 1.0  
Version Date: [11AUG2017]

Template No: CS\_TP\_BS016 Revision 4  
Effective Date: 01Apr2016

Reference: CS\_WI\_BS005

Copyright © 2009, 2010, 2012, 2016 Quintiles Transnational Corp. All rights reserved.  
The contents of this document are confidential and proprietary to Quintiles Transnational Corp. Unauthorized use, disclosure or reproduction is strictly prohibited.

TABLE AND LISTING MOCK SHELL

Listing 16.2.8.3  
Physical Examination - Abnormal Findings  
Full Analysis Population

Treatment	Subject ID/ Site ID/Age Group	Visit	Assessment Date	Area/System/ Specify (e-CRF)	Finding	Description of Finding
Vaccine	xxxxx/ xxxx/ xxxx	Screening	DDMMYYYY	Xxxxx	Abnormal-NCS	
Vaccine	xxxxx/ xxxx/ xxxx	xxxxx	DDMMYYYY	xxxxx	Abnormal-NCS	
Vaccine	xxxxx/ xxxx/ xxxx	xxxxx	DDMMYYYY	xxxxx	Abnormal-CS	xxxxxxxxx

e-CRF: Electronic Case Report Form; CS: Clinically Significant; PE: Physical Examination; NCS: Not Clinically Significant;

Programming Note: Sort by Treatment, Subject ID and Visit.

Document:	\\IEEDC-NAS01A\Biosdata\Path\IVACFLU-S\IYA06804\Biostatistics \Documentation\SAP\IVACFLU-S-0203_Mock_Listings_V1.0	Version Number:	1.0
Author:	[name]	Version Date:	[11AUG2017]

Template No: CS\_TP\_BS016 Revision 4  
Effective Date: 01Apr2016

Reference: CS\_WI\_BS005

Copyright © 2009, 2010, 2012, 2016 Quintiles Transnational Corp. All rights reserved.  
The contents of this document are confidential and proprietary to Quintiles Transnational Corp. Unauthorized use, disclosure or reproduction is strictly prohibited.

TABLE AND LISTING MOCK SHELL

Listing 16.2.8.4  
Pregnancy Report  
Full Analysis Population

Treatment	Subject ID/ Site ID/Age Group	Test Date	Date of Last Menstrual Period/ Estimated Date of Delivery	Pregnancy History	History of Fatal Anomalies/ History of Premature Births/ History of Fatal Deaths	History of Still Births/ History of Miscarriage/ Other/ Specify (e-CRF)	Medication Taken During Time of Contraception or During Pregnancy	Additional Information/ Specify (e-CRF)	Subject Willing to Contact After Delivery
Vaccine	xxxxx/ xxxx/ xxxx	DDMMYYYY	DDMMYYYY/ DDMMYYYY	Yes	No/ No/ No	No/ Yes/ No	No	Yes/ xxxxxx	Yes
Vaccine	xxxxx/ xxxx/ xxxx	DDMMYYYY	DDMMYYYY/ DDMMYYYY	Yes	Yes/ No/ No	Yes/ No/ No	No	No	Yes
Vaccine	xxxxx/ xxxx/ xxxx	DDMMYYYY	DDMMYYYY/ DDMMYYYY	No				No	Yes

Programming Note: Sort by Treatment and Subject ID.

Document: \\IEEDC-NAS01A\Biosdata\Path\IVACFLU-S\IYA06804\Biostatistics \Documentation\SAP\IVACFLU-S-0203\_Mock\_Listings\_V1.0  
 Author: [name]  
 Version Number:  
 Version Date:

1.0  
[11AUG2017]

Template No: CS\_TP\_BS016 Revision 4  
Effective Date: 01Apr2016

Reference: CS\_WI\_BS005

Copyright © 2009, 2010, 2012, 2016 Quintiles Transnational Corp. All rights reserved.  
The contents of this document are confidential and proprietary to Quintiles Transnational Corp. Unauthorized use, disclosure or reproduction is strictly prohibited.

TABLE AND LISTING MOCK SHELL

---

---

Document:	\\EEDC-NAS01A\Biosdata\Path\IVACFLU-S\IYA06804\Biostatistics \Documentation\SAP\IVACFLU-S-0203_Mock_Listings_V1.0		
Author:	[name]	Version Number:	1.0
		Version Date:	[11AUG2017]

Template No: CS\_TP\_BS016 Revision 4  
Effective Date: 01Apr2016

Reference: CS\_WI\_BS005

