### 9.1.3 Physical Examination

#### General Physical Examinations

Qualified study clinicians will conduct a physical examination of all participants at S1/D1. This physical examination will include the following:

- Recording of general appearance
- Physical examination of all organ systems. This includes the following:
  - neurologic examination, including cranial nerve examination
  - chest auscultation
  - examination of lymph nodes (axillary and cervical)
  - heart auscultation
  - abdomen palpation (to check for liver size)
- Measurement of the following vital signs:
  - body temperature
  - blood pressure
  - pulse/heart rate

\* Grade 1 elevated blood pressure (140 to < 160 mmHg systolic OR 90 to < 100 mmHg diastolic) will not be considered to be exclusionary at screening, unless judged to be clinically significant by the PI.

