**II. Definitions of terms used in the Table:**

Basic Self-care	Functions Adult Activities such as bathing, dressing, toileting, transfer/movement, continence, and feeding.
LLN	Lower limit of normal
Medical Intervention	Use of pharmacologic or biologic agent(s) for treatment of an AE
NA	Not Applicable
Operative Intervention	Surgical OR other invasive mechanical procedures.
ULN	Upper limit of normal
Usual Social & Functional Activities	Adult Adaptive tasks and desirable activities, such as going to work, shopping, cooking, use of transportation, pursuing a hobby, etc.

PARAMETER	GRADE 1 MILD	GRADE 2 MODERATE	GRADE 3 SEVERE	GRADE 4 POTENTIALLY LIFE-THREATENING
ESTIMATING SEVERITY GRADE				
Blood Pressure Abnormalities--Hypertension	140 to < 160 mmHg systolic OR 90 to < 100 mmHg diastolic	≥ 160 to < 180 mmHg systolic OR ≥ 100 to < 110 mmHg diastolic	≥ 180 mmHg systolic OR ≥ 110 mmHg diastolic	Life-threatening consequences in a participant not previously diagnosed with hypertension (e.g., malignant hypertension) OR Hospitalization indicated
SYSTEMIC				
Acute Allergic Reaction	Localized urticaria (wheals) with no medical intervention indicated	Localized urticaria with intervention indicated OR Mild angioedema with no intervention indicated	Generalized urticaria OR Angioedema with intervention indicated OR Symptoms of mild bronchospasm	Acute anaphylaxis OR Life-threatening bronchospasm OR Laryngeal edema
Chills	Symptoms causing no or minimal interference with usual social & functional activities	Symptoms causing greater than minimal interference with usual social & functional activities	Symptoms causing inability to perform usual social & functional activities	NA
Fatigue or Malaise Report only one	Symptoms causing no or minimal interference with usual social & functional activities	Symptoms causing greater than minimal interference with usual social & functional activities	Symptoms causing inability to perform usual social & functional activities	Incapacitating symptoms of fatigue or malaise causing inability to perform basic self-care functions

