2.* Body temperature (oral) [Body temperature]	[VSTEMCMP] [VSTEMP] Body temperature (oral)  °C [b] [VSTRE] Finding [A:1]  Normal [A:2]  Abnormal - NCS [A:3]  [VSTGR] Abnormal - CS Grading Scale [A:0]  Ungradable [A:1]  1 (38.0 - <38.6°C) [A:2]  2 (38.6 - <39.3°C) [A:3]  3 (39.3 - <40.0°C) [A:4]  4 (≥ 40.0°C)	
3.* Blood Pressure [Blood Pressure]	[VSBPCMP] [VSBPCOM] [SYSBP]  mmHg [b] [DIABP]  mmHg [b] Systolic Diastolic [VSBRE] Finding [A:1]  Normal [A:2]  Abnormal - NCS [A:3]  [VBSGR] Abnormal - CS Grading Scale [A:0]  Ungradable [A:1]  1 140 to < 160 mmHg systolic OR 90 to < 100 mmHg diastolic [A:2]  2 ≥ 160 to < 180 mmHg systolic OR ≥ 100 to < 110 mmHg diastolic [A:3]  3 ≥ 180 mmHg systolic OR ≥ 110 mmHg diastolic [A:4]  4 Life Threatening	
4.* Pulse Rate [Pulse Rate]	[VSHRCMP] [VSHR] Pulse Rate  beats/min [b] [VSHRE] Finding [A:1]  Normal [A:2]  Abnormal - NCS [A:3]  [HRSPEC] Abnormal - CS, Specify A200*	
Physical Examination [PE2SC]		
5.* Are there any abnormal and clinically significant PE findings? [Any abnormal and clinically significant PE findings?]	[PERES] [A:1]  Yes [A:2]  No If Yes, please complete Abnormal Findings below.	
6.*	PE number	Area/System
Abnormal Findings Entry [PE3SC]		
6.1 PE number [read-only] [PE number]	[PENUM] N3	
6.2.* Area/System [Area/System]	[PESYSPD] [A:1]  [PESYS] [cPESYS]  [A:2]  [PEDESOTH] Other, specify: A100*	
6.3.* Finding [Finding]	[PERES1] [A:1]  Abnormal, NCS [A:2]  [PECM] Abnormal, CS Please specify Current Medical Condition # A200*	
Key: [*] = Item is required [✓] = Source verification required [b] = Base Unit [*] = ASCII Only Note: Source verification critical settings made in InForm will override any settings made in Central Designer.		

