2. Body temperature (oral) [Body temperature]		
[VSTEMPCMP1] [VSTEMP1] xx.x °C[b] [VSTEMPF] Finding [A:1]  Normal [A:2]  Abnormal, NCS [A:3]  [VSTEMP1GR] Abnormal, CS Grading Scale [A:0]  Ungradable [A:1]  1 (38.0 - <38.6°C) [A:2]  2 (38.6 - <39.3°C) [A:3]  3 (39.3 - <40.0°C) [A:4]  4 (≥ 40.0°C)

3. Blood Pressure [Blood Pressure]		
[VSBPCMP2] [VSBPCMP1] [SYSBP1] [DIABP1] N3 mmHg[b] N3 mmHg[b] Systolic Diastolic [VSBPF] Finding [A:1]  Normal [A:2]  Abnormal, NCS [A:3]  [VBBPG1] Abnormal, CS Grading Scale [A:0]  Ungradable [A:1]  1 140 to < 160 mmHg systolic OR 90 to < 100 mmHg diastolic [A:2]  2 ≥ 160 to < 180 mmHg systolic OR ≥ 100 to < 110 mmHg diastolic [A:3]  3 ≥ 180 mmHg systolic OR ≥ 110 mmHg diastolic [A:4]  4 Life Threatening

4. Pulse Rate [Pulse Rate]		
[VSHRCMP1] [VSHR1] N3 beats/min[b] [VSHRF] Finding [A:1]  Normal [A:2]  Abnormal, NCS [A:3]  [VSBPSP1] Abnormal, CS Specify: A200*

Targeted Physical Examination [TPE2SC]		
5. Physical examination is not required unless subject reports symptoms. Did the subject have any symptoms that required evaluation? [Did the subject have any symptoms that required evaluation?]		
[PETVSYN1] [A:1]  Yes [A:2]  No If Yes, please complete Abnormal Findings below.

6. 	PE number	Area/System
Abnormal Findings Entry [TPE3SC]		
6.1 PE number [read-only] [PE number]		
[TPENUM] N3

6.2* Area/System [Area/System]		
[TPESYSPD] [A:1]  [TPESYS] [c]TPESYS [v] [A:2]  [TPEDESOTH] Other, specify: A200*

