 The contents of this document are confidential and proprietary to Quintiles Transnational Corp. Unauthorized use, disclosure or reproduction is strictly prohibited.

TABLE AND LISTING MOCK SHELL

Table 14.3.6.2  
Shift from Baseline to Day 8 of Vital Signs by Grade  
Full Analysis Population

Age Group: <Overall> <18-45> <46-60>

Day 8

Parameter (Unit)	Baseline	Vaccine (N=xx) n (%)				Placebo (N=xx) n (%)				Total (N=xx) n (%)			
		1	2	3	4	1	2	3	4	1	2	3	4
Body Temperature (Oral) (°C) *	1	Xx (xx.xx)	Xx (xx.xx)	Xx (xx.xx)	Xx (xx.xx)	Xx (xx.xx)	Xx (xx.xx)	Xx (xx.xx)	Xx (xx.xx)	Xx (xx.xx)	Xx (xx.xx)	Xx (xx.xx)	Xx (xx.xx)
	2	Xx (xx.xx)	Xx (xx.xx)	Xx (xx.xx)	Xx (xx.xx)	Xx (xx.xx)	Xx (xx.xx)	Xx (xx.xx)	Xx (xx.xx)	Xx (xx.xx)	Xx (xx.xx)	Xx (xx.xx)	Xx (xx.xx)
	3												
	4												

Data is based on the combined phases 2 and 3, pooled across study sites.

N= Total number of subjects in the relevant population per by-group stratification level. n= Number of subjects with available response under each group at both visit. % = Calculated relative to the total number of subjects have measurable assessment for analysis in each group at both time points.

Grades: 1- Mild; 2 - Moderate; 3 - Severe; 4 - Life-Threatening;

\*Body temperature collected in vital signs.

Source Data: Listing 16.2.8.2

Document: \\EEDC-NAS01A\Biosdata\Path\IVACFLU-S\IYA06804\Biostatistics \Documentation\SAP\IVACFLU-S-0203\_Mock\_Tables\_V1.0  
Author: [name]  
Version Number: 1.0  
Version Date: 11AUG 2017]

Template No: CS\_TP\_BS016 Revision 4  
Effective Date: 01Apr2016

Reference: CS\_WI\_BS005

Copyright © 2009, 2010, 2012, 2016 Quintiles Transnational Corp. All rights reserved.

The contents of this document are confidential and proprietary to Quintiles Transnational Corp. Unauthorized use, disclosure or reproduction is strictly prohibited.

TABLE AND LISTING MOCK SHELL

---

Programming Note: Summarize for the parameters systolic blood pressure (mmHg), diastolic blood pressure (mmHg) and pulse rate (beats/min).

---

Document:	\\EEDC-NAS01A\Biosdata\Path\IVACFLU-S\IYA06804\Biostatistics \Documentation\SAP\IVACFLU-S-0203_Mock_Tables_V1.0		
Author:	[name]	Version Number:	1.0
		Version Date:	11AUG 2017]
Template No:	CS_TP_BS016 Revision 4	Reference:	CS_WI_BS005
Effective Date:	01Apr2016		

Copyright © 2009, 2010, 2012, 2016 Quintiles Transnational Corp. All rights reserved.  

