Blood pressure (mmHg)	
 
• Normal: 90 - 120 mmHg systolic OR 60 - 85 mmHg diastolic.
 
• Abnormal - NCS: 
 
Upward trend 
 
- 121 - 139 mmHg systolic AND/OR
 
- 86 - 89 mmHg diastolic
 
 
 
Downward trend 
 
- 85-89 mmHg systolic AND/OR 50 - 59 mmHg diastolic 
 
• For the participants who have grade 1 elevated blood pressure, the Investigator will judge if it is clinically significant or not based on the medical history and physical examination, e.g., history of elevated blood pressure, blood pressure monitoring and treatment, presence of clinical signs or symptoms which need intervention, presence of risk factors (obesity, too much alcohol, tobacco use); the Investigator should also refer to the local guideline for diagnosis and treatment of high blood pressure. If the findings are clinical significant, they should be graded according to the DAIDS Table For Grading the Severity in the protocol and MOP 04.
 
• Similarly, if the participants have < 85 mmHg systolic OR < 50mmHg diastolic; the Investigator will judge it is clinically significant when the participants have clinical signs or symptoms which need intervention.
 
 
 
 
 
 
 
• For the 2 cases above, the Investigator should record the reason for his assessment in the subject binders. 
 
• Grade 2 elevated blood pressure will be judged to be clinically significant.
 
 
 
• Note: 
 
• For those who have history of elevated blood pressure, they will be judged to be non-clinically significant and enrolled according to the criterium #4 if they are stable for the past 3 months and the medication dose is stable for at least 1 month preceding vaccination.
 
• For those who have clinically significant abnormalities, the study doctor will consult and refer the participants to the health facilities for diagnosis and treatment.
 
 
 

Vital sign	Assessment criteria

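### Blood-pressure grades are recorded only when a reading is called clinically significant, so participants enrolled with Grade 1 pressure can drop out of the shift-by-grade table (Table 14.3.6.2)

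*Combined protocol and SAP*

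**What the plan says.** **What is to be reported.** SAP 17.5 lists summaries of vital signs by grade, shifts by grade and, separately, shifts by clinical significance. It does not say whether the grade is the one the investigator recorded or one derived from the reading. Mock Table 14.3.6.2, "Shift from Baseline to Day 8 of Vital Signs by Grade", has rows and columns for Grades 1 to 4 only. It counts participants with a response at both visits and names Listing 16.2.8.2 as its source.

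**How a grade comes to exist.** The footnote to the grade column of Listing 16.2.8.2 reads "a]: Applicable only for Abnormal-Clinically significant PE findings", and the sample row for a systolic reading marked abnormal but not clinically significant has an empty grade. The eCRF works the same way. On the screening examination form the blood-pressure grade opens only under one answer ("VBSGR] Abnormal - CS Grading Scale"), and so it does on the targeted examination form used at Day 8 ("VBBPG1] Abnormal, CS Grading Scale"). For Grade 1 pressure, the sheet Criteria for Marked Vital Signs Abnormalities in 16.1.10 says: "If the findings are clinical significant, they should be graded according to the DAIDS Table For Grading the Severity".

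**Who is enrolled.** Protocol 9.1.3, repeated in SAP 17.6, says that Grade 1 elevated pressure "will not be considered to be exclusionary at screening, unless judged to be clinically significant by the PI". For participants with a history of raised pressure who are stable, the criteria sheet says "they will be judged to be non-clinically significant and enrolled according to the criterium #4".

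**What a grade means.** Protocol Appendix A defines Grade 1 hypertension by the number alone: "140 to < 160 mmHg systolic OR 90 to < 100 mmHg diastolic". Clinical significance is not part of the definition.

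**The concern.** Appendix A and section 9.1.3 treat grade and clinical significance as two separate things: a reading can be Grade 1 and not clinically significant. The eCRF and the listing join them, because a grade is recorded only once the reading has been called clinically significant. The enrolment rule then works against this gate. A participant who enters properly with Grade 1 pressure is one whose reading was judged not clinically significant, and so one for whom no grade was recorded.

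If Table 14.3.6.2 is built from that recorded grade, its baseline Grade 1 row for blood pressure is empty by construction for participants enrolled under the rule. The criteria sheet always calls a Grade 2 reading clinically significant, so worsening to Grade 2 at Day 8 would be graded at Day 8 but have no baseline grade to be paired with. The table would then be silent about the participants whose pressure was already raised at entry.

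**Working it through.** The plan states no figure on this point, so the check traces example readings through the rules.

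**Inputs.** Appendix A cut-offs, taking the highest grade met by either component:

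- Grade 1: systolic 140 to under 160, or diastolic 90 to under 100.
- Grade 2: systolic 160 to under 180, or diastolic 100 to under 110.
- Grade 3: systolic 180 or more, or diastolic 110 or more.
- Anything lower is written here as 0.

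**Recorded grade** = Appendix A grade if the reading is called clinically significant (CS), otherwise none. **Derived grade** = Appendix A grade whatever the call. A pair has a cell in Table 14.3.6.2 only if both grades lie in 1 to 4. NCS means not clinically significant.

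| Baseline | Day 8 | Recorded | Cell? | Derived | Cell? |
|---|---|---|---|---|---|
| 150/85 NCS | 150/85 NCS | none→none | no | 1→1 | yes |
| 150/85 NCS | 150/85 CS | none→1 | no | 1→1 | yes |
| 150/85 NCS | 165/95 CS | none→2 | no | 1→2 | yes |
| 150/85 NCS | 182/95 CS | none→3 | no | 1→3 | yes |
| 150/85 NCS | 118/75 NCS | none→none | no | 1→0 | no |
| 118/75 NCS | 150/85 CS | none→1 | no | 0→1 | no |
| 118/75 NCS | 150/85 NCS | none→none | no | 0→1 | no |
| 118/75 NCS | 118/75 NCS | none→none | no | 0→0 | no |

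(For 118/75, NCS here simply means not called CS.)

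**Reading the table.** Rows 1 to 4 are the loss caused by the gate: with recorded grades none has a cell, and with derived grades all four do. Rows 5 to 8 are lost under either method because the shell has no Grade 0 level. The gate and the missing level are therefore separate causes, and both need attention.

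**Other vital signs.** For temperature, Grade 1 starts at 38.0 °C and the criteria sheet calls every reading of 38.0 °C or more clinically significant, so the gate removes no temperature grade. For pulse rate, the criteria sheet says there is no grading scale and SAP 17.5 mentions grading only for temperature and blood pressure, yet the programming note of Table 14.3.6.2 asks for pulse rate.

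**Can the grade be derived?** Yes. The eCRF stores systolic and diastolic pressure as numbers at screening and on the targeted examination form, whatever the significance call.

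**Scale, for illustration only.** The 46–60 stratum has 126 + 318 = 444 planned participants. If 10% to 25% of them had a Grade 1 reading at baseline, which is an assumption with no support in the documents, 0.10 × 444 ≈ 44 to 0.25 × 444 = 111 would lack a baseline grade. That counts ungraded participants, not lost changes in grade.

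**The case against.** The strongest reply is that the error is conditional. The footnote describes how the investigator's grade was collected. The same listing has a numeric result for every reading, Appendix A grades on the number, and SAP 17.5 nowhere confines grades to clinically significant findings. A programmer could derive the grade and the gap would not arise. This stands: the plan leaves a derivation unspecified, and the loss follows only if the recorded grade is used. But the listing named as the source and the eCRF both point to the recorded grade, and nothing in the SAP points the other way.

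It can also be said that little is hidden. Table 14.3.6.1 gives actual values and changes, Table 14.3.6.3 gives normal, NCS and CS shifts, and the listing prints every value. This largely stands. A rise from 118/76 to 155/98 called NCS would appear in Table 14.3.6.3 as normal to NCS. The cover is incomplete, however: the NCS category takes in systolic 121–139 as well as Grade 1 readings judged NCS, so a rise from 125 to 155 with both readings NCS shows there as no change.

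A reader might infer that Table 14.3.6.2 would print false shifts, for example an unchanged 150/95 called CS only at Day 8 appearing as a new Grade 1. The shell does not allow it. It has no ungraded or normal row, so that participant is missing, not misplaced. A false 0→1 could arise only if a Grade 0 row were added and ungraded readings were put in it without deriving grades.

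Finally, significance is judged under double-blind conditions, so there is no evident reason for the gate to bias one arm against the other.

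**Conclusion.** The point holds for blood pressure and for this one table. If Table 14.3.6.2 uses the recorded grade, participants enrolled with Grade 1 pressure under section 9.1.3 and the criteria sheet have no baseline grade, and true shifts from Grade 1 to Grade 1, 2 or 3 are left out. The conclusion assumes that the eCRF gate and the enrolment rule are followed as written, and that the baseline reading is either the screening reading or a Day 1 reading at which eligibility is reconfirmed.

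It does not extend to all vital-sign grades, since temperature loses nothing. Nor does it mean that no baseline blood-pressure grade can exist: a Grade 2 reading is to be judged clinically significant and would be graded, and the exclusion list does not name it.

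The consequence is modest. Vital-sign shifts are descriptive and are not among the four primary safety endpoints, and no licensure criterion depends on them. The number of participants affected cannot be obtained from the documents. The correction is still worth making, because a planned table would otherwise fail to show what its title promises for participants already raised at baseline, and the data to repair it are already collected.

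**What to change.** 1. In SAP 17.5 and Table 14.3.6.2, state that blood-pressure grades at baseline and Day 8 are derived from the recorded systolic and diastolic values by the Appendix A cut-offs, whatever the significance call.
2. Add Grade 0 and missing levels to the rows and columns of the shell, so that new-onset and resolving shifts have a cell. Do this together with step 1; a Grade 0 level without derived grades would open the way to the false shifts described above.
3. Base the denominator on participants with a reading at both visits, not on those with a grade at both.
4. Remove pulse rate from this table.
5. In Listing 16.2.8.2, show the derived grade beside the investigator-recorded one. The footnote can stay on the recorded column.
6. Leave clinical significance in Table 14.3.6.3.

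The cost is a sentence in the SAP, one derived variable, and edits to one table shell and one listing shell. No eCRF change and no new data are needed.
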